### **4.3 METHOD OF TREATMENT ASSIGNMENT AND BLINDING**

Randomization will be performed centrally using an interactive voice/Web response system (IxRS) that uses stratified block randomization. After screening, patients who meet all eligibility criteria will be randomly assigned to 1 of 2 treatment groups (crenezumab or placebo). Patients will be randomized in a drug to placebo ratio of 1:1.

Randomization to treatment allocation will also be stratified by dementia status (pAD vs. mAD), patient *APOE* $\epsilon$ 4 status (presence or absence of  $\epsilon$ 4 allele), background medication at baseline (present, absent) and geographic region. Stratification factors will ensure balance of these strong prognostic factors across treatment arms and facilitate unbiased estimate of treatment effect in subgroups based on disease severity and geographic regions.

Except in circumstances in which a health authority, Ethics Committee (EC), or IRB requires the patient be told of his or her *APOE* status, patients, investigators, central MRI reader, and the cognitive test rater as well as the Sponsor *will be blinded to individual patient APOE genotype results*. *APOE* status information will be supplied directly to the IxRS vendor by the central testing laboratory so that the information can be incorporated at the time of randomization. In cases where *APOE* status is already known, these prior results will be blinded to the Sponsor and as much as possible to the site and central MRI reader.

The study is to be conducted in a double-blind manner to minimize potential bias from investigators and patients. The Sponsor will be blinded to study treatment. The Master Randomization or Master Medication List will not be available at the study center, to Roche monitors, project statisticians, or to the project team at Roche with the exception of those responsible for performing PK, PD, and *ADA* assessments. Personnel responsible for performing PK, PD and *ADA* assessments will be unblinded to patients' treatment assignments to identify appropriate samples to be analyzed. Samples from patients assigned to the placebo group will not be analyzed except by request (e.g., to evaluate a possible error in dosing).

If unblinding is necessary for patient management (e.g., in the case of a serious adverse event for which patient care might be affected by knowledge of treatment assignment), the investigator will be able to break the treatment code by contacting the IxRS. Treatment codes should not be broken except in emergency situations. If the investigator wishes to know the identity of the study treatment for any other reason, he or she should contact the Medical Monitor directly. The investigator should document and provide an explanation for any premature unblinding (e.g., accidental unblinding, unblinding due to a serious adverse event).

For regulatory reporting purposes, and if required by local health authorities, the Sponsor will break the treatment code for all serious, unexpected suspected adverse reactions that are considered by the investigator or Sponsor to be related to study drug.

#### **4.4 STUDY TREATMENT**

The investigational medicinal product (IMP) for this study is crenezumab.

#### **4.4.1 Formulation, Packaging, and Handling**

##### **4.4.1.1 Crenezumab and Placebo**

Crenezumab and placebo will be supplied by the Sponsor as a solution buffered at pH 5.5 (using arginine succinate solution that contains polysorbate 20 and water for injection) in 6.0 mL glass vials. For information on formulation and handling of crenezumab, see the pharmacy manual and crenezumab Investigator's Brochure.

#### **4.4.2 Dosage, Administration, and Compliance**

##### **4.4.2.1 Crenezumab and Placebo**

Crenezumab or placebo will be administered via IV infusion to all patients. Those randomized to the active arm will receive crenezumab at a dose of 60 mg/kg q4w for 26 doses.

For all infusions (crenezumab and placebo), IV infusions will be administered by appropriately trained staff in the clinic or other agreed environment (e.g., the patient's home); the first four infusions of study drug must be administered at the clinic.

The IV drug will be prepared and infused from the IV bag by infusion pump. The bag size, drug preparation, and infusion rates are all described in the pharmacy manual guidance. All patients will be monitored for a minimum of 1 hour after dosing, and vital signs will be measured immediately following completion of the infusion and  $\geq 60$  minutes after the end of the infusion as described in the pharmacy manual.

For the IV dose calculation, the patient's screening weight (reference weight) should be used. If the current weight changes by  $\geq 10\%$ , the current weight should become the new reference weight for subsequent dosing. If the patient's weight changes again by  $\geq 10\%$  from the reference weight, the IV dose should again be recalculated. See the pharmacy manual for further information.

Crenezumab will be administered to patients under close medical supervision in a setting with access to appropriate emergency equipment and staff who are trained to monitor and respond to medical emergencies. In the event that a patient experiences a mild infusion-related reaction, the infusion will be halted. Once the reaction has resolved, the infusion rate will be resumed at half of the most recently used rate [REDACTED]. Patients who experience a moderate infusion-related reaction (e.g., fever or chills) should have the infusion stopped immediately and should receive aggressive symptomatic treatment. The infusion should not be restarted before all symptoms have disappeared, and then it should be restarted at half the initial rate. Patients who experience serious or severe hypersensitivity reactions (e.g., hypotension, mucosal involvement) should not receive additional study drug. In any patient who develops anaphylaxis, anaphylactoid, or serious hypersensitivity reactions, a blood sample will be collected for analyses of antibodies to crenezumab and/or other components of the drug product. In addition, for any patient suspected of developing anaphylaxis, or anaphylactoid or serious hypersensitivity reactions warranting

discontinuation of dosing, a washout ADA sample (16 weeks post-dose) and concurrent PK sample must be collected.

Any overdose or incorrect administration of study drug should be noted on the Study Drug Administration eCRF. Adverse events associated with an overdose or incorrect administration of study drug should be recorded on the Adverse Event eCRF.

At applicable sites, following the first four infusions, study drug may be administered by a trained home nursing (HN) professional at the patient's home or another suitable location, if the patient has given written informed consent to participate in HN visits (please refer to Section 4.6 for details).

#### **4.4.2.2 Non-Investigational Medicinal Products**

All patients who are enrolled using PET amyloid evaluation at baseline and those in any relevant substudies will be assessed by PET imaging using an appropriate PET ligand. Details of substudies are described in separate protocols.

*According to EU guidance, the PET ligands used in the context of this study (and associated substudies) have been designated as non-IMPs. In some regions, according to local regulations, these PET tracers may be considered as IMPs.*

*Regarding the safety profile of and reporting requirements for the PET ligands administered in this study (and associated substudies) please refer to Section 5.7.*

#### **4.4.3 Investigational Medicinal Product Accountability**

All IMPs required for completion of this study (crenezumab or placebo) will be provided by the Sponsor where required by local health authority regulations. The study site will acknowledge receipt of IMPs, using the IxRS to confirm the shipment condition and content. Any damaged shipments will be replaced.

IMPs will either be disposed of at the study site according to the study site's institutional standard operating procedure or returned to the Sponsor with the appropriate documentation. The site's method of IMP destruction must be agreed to by the Sponsor. The site must obtain written authorization from the Sponsor before any IMP is destroyed, and IMP destruction must be documented on the appropriate form.

Accurate records of all IMPs received at, dispensed from, returned to, and disposed of by the study site should be recorded on the Drug Inventory Log.

#### **4.4.4 Post-Trial Access to Crenezumab**

The Sponsor will offer post-trial access to the study drug (crenezumab) free of charge to eligible patients in accordance with the Roche Global Policy on Continued Access to Investigational Medicinal Product, as outlined below.

A patient will be eligible to receive study drug after completing the study if all of the following conditions are met:

- The patient has a life-threatening or severe medical condition and requires continued study drug treatment for his or her well-being
- There are no appropriate alternative treatments available to the patient
- The patient and his or her doctor comply with and satisfy any legal or regulatory requirements that apply to them

A patient will not be eligible to receive study drug after completing the study if any of the following conditions are met:

- The study drug is commercially marketed in the patient's country and is reasonably accessible to the patient (e.g., is covered by the patient's insurance or wouldn't otherwise create a financial hardship for the patient)
- The Sponsor has discontinued development of the study drug or data suggest that the study drug is not effective for AD
- The Sponsor has reasonable safety concerns regarding the study drug as treatment for AD
- Provision of study drug is not permitted under the laws and regulations of the patient's country

The Roche Global Policy on Continued Access to Investigational Medicinal Product is available at the following Web site:

[http://www.roche.com/policy\\_continued\\_access\\_to\\_investigational\\_medicines.pdf](http://www.roche.com/policy_continued_access_to_investigational_medicines.pdf)

## **4.5 CONCOMITANT THERAPY**

Concomitant therapy includes any medication (e.g., prescription drugs, over-the-counter drugs, herbal/homeopathic remedies, nutritional supplements) used by a patient 3 months prior to screening through the study completion/early termination visit. All concomitant medications should be reported to the investigator and recorded on the Concomitant Medications eCRF page.

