
 
To evaluate the efficacy of crenezumab compared with placebo on events related to disease progression
 
	
 
Effect on cognition, assessed by time to an increase from baseline at any time before or on Week 105 (i.e., worsening) on a version of the ADAS-Cog or the MMSE
 
Time to clinically evident decline since baseline, as defined by an increment on the CDR global score
 
Time to development of impairment in additional domains or worsening of impairment within a domain on the CDR-SB
 
Time to increase-of-dependence level, as derived from the ADCS-ADL scale
 
Time to decline in ability to perform one or more basic or instrumental ADL present at baseline using the ADCS-ADL scale
 
Composite time-to-event endpoint. Combination of clinical progression events including any of the following: worsening disease severity (e.g., CDR Global), increasing care needs (e.g., ADCS-ADL derived dependence level), concomitant medications, and other events that may be indicative of disease progression.
 

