#### **3.3.2 Rationale for Long-Term Follow-Up**

The primary objective of the long term follow-up is to estimate the long-term safety of crenezumab. Assessments performed 16 and 52 weeks after the last dose of treatment will evaluate the effects of treatment on both efficacy and safety parameters over an extended period when no study drug is administered. These assessments will be conducted in all patients who discontinue treatment *early* or who complete the study but do not enter the OLE. These assessments will allow for the exploration of the long-term effects of exposure to study drug given that continued cognitive decline is expected in this patient population.

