- Deformity of the lumbosacral region of the spine that in the opinion of the investigator would contraindicate lumbar puncture in those who can only be CSF-eligible due to regional lack of availability of PET ligands.
- Clinically significantly abnormal screening blood or urine that remain abnormal at retest
- Impaired coagulation (screening PT > 1.2 × the ULN that remains abnormal on retest).
- Known history of severe allergic, anaphylactic, or other hypersensitivity reactions to chimeric, human, or humanized antibodies or fusion proteins
- Any other severe or unstable medical condition that, in the opinion of the investigator or Sponsor, could be expected to progress, recur, or change to such an extent that it could put the patient at special risk, bias the assessment of the clinical or mental status of the patient to a significant degree, interfere with the patient’s ability to complete the study assessments, or would require the equivalent of institutional or hospital care
- Residence in a skilled nursing facility such as a convalescent home or long-term care facility: Patients who subsequently require residence in these facilities during the study may continue in the study and be followed for efficacy and safety provided that they have a caregiver who meets the minimum requirement (refer to Section 4.1).

The following medications are prohibited for a pre-specified duration prior to study start, as indicated, and during the entire period of study participation (patients who start these medications during the study may be withdrawn from study treatment):

- Any previous administration of crenezumab or any other therapeutic that targets A $\beta$
- Any investigational active immunotherapy (vaccine) that is under evaluation to prevent or postpone cognitive decline

- Any passive immunotherapy (immunoglobulin) or other long-acting biologic agent that is under evaluation to prevent or postpone cognitive decline within 1 year of screening
- Any other investigational treatment within 5 half-lives or 3 months of screening, whichever is longer
- Any previous treatment with medications specifically intended to treat Parkinsonian symptoms or any other neurodegenerative disorder within 1 year of screening
  - Certain medications are acceptable if the patient is taking the medicine for a non-neurodegenerative disorder, such as restless leg disorder (e.g., pramipexole)

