#### **4.6.8.2 Study Assessments**

In order to be randomized to receive double-blind treatment, patients must have no significant change in medical, psychiatric or neurological conditions or change in medication since screening. The recommended order of assessments and rating scales is as follows:

- Clinical assessments (e.g., QoL-AD, ZCI-AD, MMSE; ADAS-Cog-13; ADCS-ADL; CDR), including all those that require caregiver input, should be completed before any invasive safety assessments

- Vital signs; ECGs; blood draws for clinical laboratory assessments, pharmacokinetics, *ADA*, and plasma biomarkers; and urine samples are recommended to be collected following scale assessments and must be collected before study drug administration.

The recommended order of clinical assessments/rating scales at baseline, on treatment, and at the Week 105 (or early termination) visit is as follows:

Patient	Caregiver
1. ADAS-Cog-13	1. CDR (caregiver input)
2. CDR (patient interview)	2. ADCS-ADL
3. MMSE	3. FAQ
4. FCSRT	4. EQ-5D
5. QoL-AD (if appropriate)	5. ZCI-AD (if appropriate)
6. C-SSRS	6. QoL-AD(if appropriate)
	7. NPI-Q(if appropriate)

ADAS-Cog-13=Alzheimer’s Disease Activity Scale-Cognitive (subscale) 13;  
 ADCS-ADL = Alzheimer’s Disease Cooperative Study-Activities of Daily Living;  
 C-SSRS=Columbia-Suicide Severity Rating Scale; CDR=Clinical Dementia Rating;  
 FAQ=Functional Activities Questionnaire; FCSRT=Free and Cued Serial Recall Task;  
 MMSE=Mini Mental State Examination; NPI-Q=Neuropsychiatric Inventory-Questionnaire;  
 QoL-AD=Quality of Life-Alzheimer’s Disease; ZCI-AD= Zarit Caregiver Interview-Alzheimer’s Disease.

Vital signs, ECGs, blood draws for clinical laboratory assessments, pharmacokinetics, *ADA*, plasma biomarkers, and urine samples are recommended to be collected following scale assessments and must be collected before study drug administration.

If assessments are split over 2 days, all safety assessments must be done on same day as the infusion.

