## Appendix 1 Schedule of Assessments (cont.)

Assessment/ Procedure	Screen	BL		Treatment Period													ET
		Day 1 Wk1	Day 2 Wk 1	Wk 5	Wk 9	Wk 13	Wk 17	Wk 21	Wk 25	Wk 29	Wk 33	Wk 37	Wk 41	Wk 45	Wk 49	Wk 53	
Dose Number		1 a		2	3	4	5 b	6 b	7 a	8 b	9 b	10	11 b	12 b	13 b	14 a	a
MRI q	x					x r			x r			x r				x r	x
PET / CSF sample q, s	x															x w, x	x w, x
CDR	x	x							x							x	x
ADAS-Cog-13	x	x							x							x	x
ADCS-ADL; FAQ		x							x							x	x
MMSE	x t	x							x							x	x
NPI-Q		x														x	x
FCSRT-IR	x t	x							x							x	x
EQ-5D		x							x							x	x
QOL-AD		x														x	x
ZCI-AD		x														x	x
C-SSRS BL/SLV u		x							x							x	x
Concomitant medications		x	x	x	x	x	x	x	x	x	x	x	x	x	x	x	x
Adverse events		x	x	x	x	x	x	x	x	x	x	x	x	x	x	x	x
Study drug administration v		x		x	x	x	x	x	x	x	x	x	x	x	x	x	

ACDS-ADL = Alzheimer's Disease Cooperative Study – Activities of Daily Living; AD = Alzheimer's disease; ADAS-Cog13 = Alzheimer's Disease Activity Scale Cognition (subscale) 13; BL = baseline; CDR = Clinical Dementia Rating; CSF = cerebrospinal fluid; C-SSRS= Columbia Suicide Severity Rating Scale; ET = early termination; FAQ = Functional activities Questionnaire ; FCSRT-IR = Free and Cued Selective Reminding Test–Immediate Recall; MMSE = Mini-Mental State Examination; MRI = magnetic resonance imaging; NPI-Q = Neuropsychiatric Inventory Questionnaire; PET = positron emission tomography; PK = pharmacokinetic; QoL-AD = Quality of Life–Alzheimer's Disease; SLV = since last visit; Wk = week; ZCI-AD = Zarit Caregiver Interview for Alzheimer's Disease.

**Note:** The visit window is  $\pm 7$  days for dosing days and  $\pm 3$  days for all other visits. Patients should return to initial planned schedule per randomization for subsequent visits. For patients who terminate early, assessments listed in the ET visit (week 105) should be completed.

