## Appendix 1 Schedule of Assessments (cont.)

Assessment/Procedure	Treatment Period												Follow-up for those not entering OLE		
	Wk 57	Wk 61	Wk 65	Wk 69	Wk 73	Wk 77	Wk 81	Wk 85	Wk 89	Wk 93	Wk 97	Wk 101	Wk 105 +4 wks (or ET)	Wk 117 +16 wks	Wk 153 +52 wks
Dose number	15 a	16 a	17 a	18 a	19 a	20 b	21 a	22 a	23 a	24 a	25 a	26 a	b, c		
C-SSRS SLV						X							X		
Concomitant medications	X	X	X	X	X	X	X	X	X	X	X	X	X		
Adverse events	X	X	X	X	X	X	X	X	X	X	X	X	X		
Study drug administration m	X	X	X	X	X	X	X	X	X	X	X	X			

ACDS-ADL=Alzheimer's Disease Cooperative Study – Activities of Daily Living; ADAS-Cog13 = Alzheimer's Disease Activity Scale Cognition (subscale) 13; CDR= Clinical Dementia Rating; C-SSRS= Columbia Suicide Severity Rating Scale; ET=early termination; FAQ = Functional activities Questionnaire; FCSRT-IR = Free and Cued Selective Reminding Test–Immediate Recall; MMSE = Mini-Mental State Examination; MRI = magnetic resonance imaging; NPI-Q= Neuropsychiatric Inventory-Questionnaire; OLE = open-label extension; QOL-AD = Quality of Life–Alzheimer's Disease; SLV = since last visit; Wk = week; ZCI-AD = Zarit Caregiver Interview for Alzheimer's Disease.

**Note:** The visit window is  $\pm 7$  days for dosing days and  $\pm 3$  days for all other visits. Patients should return to initial planned schedule per randomization for subsequent visits. For patients who terminate early, assessments listed in the ET visit should be completed.

In case of rescreening a patient, all screening assessments must be repeated other than the MRI (if performed within 8 weeks of randomization), lumbar puncture and amyloid PET scan if previous results were within eligible ranges.

a Visit suitable for home administration of crenezumab.

b Visit may be split over 2 days. All cognitive and functional assessments should be completed first. All safety assessments (e.g., visits, blood tests, and ECGs) should be completed on the day of dosing.

c Transition to OLE protocol for those eligible to participate.

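### Concomitant medications are not scheduled at the +16- and +52-week visits where off-drug efficacy is measured, and Section 4.5 does not define when recording ends

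*Combined protocol and SAP*

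**What the plan says.** - **Recording window.** Protocol Section 4.5 defines concomitant therapy as anything "used by a patient 3 months prior to screening through the study completion/early termination visit". The closing visit is not tied to a week.
- **Schedule.** In Appendix 1 Table 2 (Year 2) the row "Concomitant medications" is marked at every visit from Week 57 to Week 105/ET. It is empty in the last two columns, Wk 117 (+16 weeks) and Wk 153 (+52 weeks). CDR, ADAS-Cog-13, ADCS-ADL/FAQ, MMSE, EQ-5D and QOL-AD are marked in both.
- **Purpose of those visits.** Section 3.3.2 names long-term safety as the primary objective, and adds that the assessments "will evaluate the effects of treatment on both efficacy and safety parameters over an extended period when no study drug is administered".
- **Medication rules.** Section 4.5.1 lets a medication be added or its dose changed after randomization when medically indicated. Section 4.2 prohibits listed drugs, including other therapeutics that target amyloid beta, before study start "and during the entire period of study participation".

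**The concern.** The off-drug visits measure cognition and function in patients who no longer receive study drug and are not in the OLE. Symptomatic AD medication may be started or changed in that period. Without a record of it, a difference between arms at +16 or +52 weeks, or a convergence of the arms, could reflect the earlier study treatment or the new medication, and the data could not show which. A start of prohibited anti-amyloid therapy would also go unseen, although that is the less likely case. What is at stake is the interpretation of the exploratory off-drug efficacy data, not the trial's main result.

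**Working it through.** The plan gives no figure on this point, so the check is a comparison of texts plus some visit arithmetic.

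**1. The schedule rows.** Appendix 1 Table 2 has 15 visit columns: twelve dosing visits (Wk 57 to Wk 101), Wk 105/ET, Wk 117 and Wk 153.

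| Row | Columns marked | Marked at +16 / +52 weeks |
|---|---|---|
| Concomitant medications | 13 of 15 (Wk 57 to Wk 105/ET) | 0 of 2 |
| CDR | Wk 77, 105/ET, 117, 153 | 2 of 2 |
| ADAS-Cog-13 | Wk 77, 105/ET, 117, 153 | 2 of 2 |
| ADCS-ADL; FAQ | Wk 77, 105/ET, 117, 153 | 2 of 2 |
| MMSE | Wk 77, 105/ET, 117, 153 | 2 of 2 |
| EQ-5D, QOL-AD | Wk 77, 105/ET, 117, 153 | 2 of 2 |

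**2. When Section 4.5 stops.** Two readings are possible.

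- *Week 105/ET.* Section 4.6.8.2 pairs early termination with Week 105: its order of scales at baseline, "on treatment, and at the Week 105 (or early termination) visit is as follows". The note to Appendix 1 Table 1 does the same for patients who terminate early: "assessments listed in the ET visit (week 105) should be completed". Section 3.3.2 says the off-drug assessments are for patients who stop early "or who complete the study but do not enter the OLE", which places completion before the follow-up. On this reading nothing is recorded at +16 or +52 weeks.
- *Week 153.* Section 3.2 puts the last visit for patients not entering the OLE at 153 weeks. On this reading Section 4.5 requires recording that the schedule omits, and the two must be reconciled.

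Both readings lead to the same correction.

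**3. Could adverse-event reporting fill the gap?** Section 5.3.1 ends it 8 weeks after the last dose. For a completer last dosed at Week 101 that is 101 + 8 = Week 109. The follow-up visits are at 101 + 16 = Week 117 and 101 + 52 = Week 153, both later. In general 8 < 16 < 52, so the window closes before either visit whenever dosing stopped.

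**4. Who is exposed?**
- *Completers who decline the OLE.* Their last scheduled medication record is at Week 105, so both later visits lack one.
- *Early stoppers who keep attending regular visits.* Medications are marked at each of those visits, so a follow-up visit that falls before Week 105 is covered by the record around it. For example, with a last dose at Week 49 the visits fall at 49 + 16 = Week 65 and 49 + 52 = Week 101.
- *Early stoppers who return only for the post-dose visits.* After ET they have rating scales but no scheduled medication record.

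Sizing these groups needs OLE uptake and attendance after stopping. The protocol gives neither.

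**The case against.** **The visits are mainly for safety.** Section 3.1.1 describes them as primarily for safety with limited efficacy assessment, and Section 3.3.2 speaks of exploring long-term effects. No Table 1 efficacy endpoint is set at +16 or +52 weeks, and Section 6 plans no analysis there. This stands, and it limits the importance of the point. It does not remove it: the scales are collected for a stated efficacy purpose, and a medication record helps read the safety data too.

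**A blank cell does not prove non-collection.** The adverse-event row also stops at Week 105/ET, although Section 5.3.1 carries reporting further. That is fair. But adverse events have explicit text extending the window, whereas concomitant medication has only the undefined end point in Section 4.5.

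**Early stoppers are largely covered.** They are encouraged to attend subsequent visits, especially Week 105. This stands for those who do so.

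**Anti-amyloid therapy is unlikely.** It is prohibited, and Section 3.3.5 notes that no disease-modifying compound was approved. This also stands, so symptomatic medication is the realistic concern. The only stated consequence of prohibited use is possible withdrawal from study treatment (Section 4.5.2), which no longer matters once dosing has ended. The interest is therefore interpretive rather than disciplinary.

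**Three stronger inferences are tempting, and the documents do not support them.**
- *Bias in the exploratory composite.* Table 1 lists among its events "increasing care needs (e.g., ADCS-ADL derived dependence level), concomitant medications, and other events that may be indicative of disease progression", so a reader might infer that early stoppers seen only after dosing can have CDR or ADL events but not medication events. The event definitions are deferred to the SAP. Nothing shows that +16- or +52-week scores enter the composite, or that stopping differs by arm.
- *A head count from dropout.* Section 6.1 assumes 35% dropout, and 0.35 × 750 = 262.5. That counts patients lost by Week 105. Those who never return have no follow-up scores to confound, and completers who decline the OLE are not in it.
- *A head count from the calendar.* Of the 25 possible early last-dose visits (Weeks 1 to 97), the +16-week visit falls by Week 105 for (89 − 1)/4 + 1 = 23, and the +52-week visit for (53 − 1)/4 + 1 = 14. These count dosing weeks, not patients, and ignore the medication record kept at regular visits.

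**Conclusion.** The point holds as a gap in the schedule with an undefined end point in Section 4.5. Following Appendix 1 as written, off-drug efficacy at +16 and +52 weeks cannot be separated from new or changed symptomatic AD medication or, less likely, from prohibited anti-amyloid therapy.

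It affects a secondary, exploratory aim only. The primary and key secondary analyses at Week 105 are not affected. The documents do not allow a count of the patients concerned, and they do not show that patients off study drug start other treatment more often than others.

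The conclusion assumes that sites collect what the schedule marks. If another study document already requires the record, the protocol text still needs aligning. This is a cheap improvement worth making rather than a flaw that threatens the trial.

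**What to change.** 1. In Appendix 1 Table 2, mark concomitant medications in the Wk 117 (+16 weeks) and Wk 153 (+52 weeks) columns.
2. In Section 4.5, state that recording continues through the last study visit the patient attends, post-treatment follow-up included.
3. Beside any summary of off-drug efficacy, show starts of symptomatic AD drugs and of anti-amyloid therapy by arm.

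The cost is two schedule cells, one sentence and one small table. The visits and the Concomitant Medications eCRF page already exist, so the burden is a little extra data entry and cleaning. Starts that go unrecorded may be hard to reconstruct later.
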